Study Protocol with SAP

Improving Satisfaction, Engagement and Outcomes Among Traditionally Underserved Children
Through Cultural Formulation

NCT03499600

PI: [name]
Project Mentor: [name]

Document Date: 8/10/22

Objectives

The present randomized examination evaluated the incremental utility of augmenting Clinical Assessment with the CFI among culturally diverse families seeking services for child-externalizing problems. Initial analyses examined equity-informed implementation outcomes – i.e., CFI fidelity, clinical utility, caregiver feeling understood and satisfaction – which can inform broader CFI use, sustainability, and ultimate effects on inequities (Eccles & Mittman, 2006; Proctor et al., 2011; Woodward et al., 2019). Given the tendency for families from marginalized backgrounds to feel misunderstood by their provider, initial analyses examined caregiver and provider perceptions at post-assessment regarding the extent to which the provider understood the family's values and what is important to them. Next, analyses examined the effects of the CFI on subsequent treatment engagement and ultimate clinical response. Treatment engagement was conceptualized through family behaviors (e.g., attendance and homework) and the family-provider relationship (Becker et al., 2018). We first hypothesized that incorporating the CFI would be clinically useful, that providers and caregivers would report high satisfaction with the CFI, and that they would perceive the CFI as fostering improved provider understanding of the family's values. We further hypothesized that caregivers randomized to receive the CFI as part of their child's intake assessment, relative to caregivers randomized to standard Clinical Assessment (CA), would show stronger subsequent treatment engagement (i.e., higher subsequent treatment session attendance, homework completion, working alliance, and first treatment module completion), and would show higher rates of ultimate treatment response. Exploratory analyses further examined whether the language of service delivery (English versus Spanish) moderated outcomes. Families receiving services in Spanish, may be particularly vulnerable to poor treatment engagement and outcomes due to lower levels of acculturation, and potential misalignment of mental with their background and explanatory models (Alegria et al., 2015; Burnett-Ziegler et al., 2018; Ho et al., 2007; La Roche, 2013; Yeh et al., 2005). Moreover, there is evidence that culturally adapted EBPs are more effective for families with lower levels of acculturation and those that receive services in their native language (Griner & Smith, 2006).

Methods

Participants

Participants were 89 children ages 2–7 ($M = 5.10$, $SD = 1.6$), and their primary caregivers ages 20–57 ($M = 33.4$, $SD = 7.3$) receiving services through a Miami- Dade County-funded initiative to provide free behavioral parenting intervention services to underserved communities (i.e., those with limited access to mental health services) and to assess various engagement strategies. The majority of primary caregivers were mothers ($N = 85$). The initiative serves English- and Spanish-speaking families of children with behavior problems (clinically elevated symptoms) and/or history of child maltreatment. Comorbid child disorders did not exclude eligibility, although caregivers actively abusing illegal substances were not eligible. There were no other exclusion criteria. Approximately two- thirds of the children were male and approximately 89% of the children were identified as a member of a racial and/or ethnic minority group by the caregiver. Sixty percent of participating caregivers did not have a college degree. Roughly half of the families (54.8%) had significant financial needs and fell in “extreme poverty,” “poor,” or “low-income” economic ranges (see Measures). Regarding housing security, roughly one-third of participating families lived with more than two people per bedroom, and roughly one-fifth reported temporarily living with others due to economic difficulties. Nearly 33% of families received treatment and study activities in Spanish.

Procedures

This study was approved by the University of Miami and the Florida International University Institutional Review Boards. All services were provided in English or Spanish. Presenting families completed informed consent, then were randomized across two parallel pre-treatment

assessment conditions: Clinical Assessment (CA) or CFI followed by CA (CFI+CA). A master random number table generator was used for randomization. Services were offered across three sites. The intake assessment included consent, an intake interview (CA or CFI+CA), completion of study questionnaires, and structured observations of parent–child interactions, generally over 2–3 one-hour sessions. Families were not informed of the assessment condition to which they were randomized. After intake assessment, patients were offered a course of Parent-Child Interaction Therapy (PCIT), a well-supported behavioral parenting intervention for child behavior problems and maladaptive family patterns (Eyberg & Funderburk, 2011). A full PCIT course entails completion of two sequential treatment modules; the first module teaches caregivers to use positive and differential social attention to improve child behavior and the parent–child relationship, and the second module teaches caregivers consistent limit setting and effective discipline strategies. The precise length of a PCIT course varies as a function of the quickness with which parents acquire the skills and the child's behavior falls within normal limits. The standard PCIT protocol was flexibly delivered across conditions. A power analysis assuming an alpha level = 0.05, beta = 0.2, and power = 0.8, identified a sample ≥ 82 participants was needed to identify small-to-medium effects (i.e., OR~2.5). Recruitment was closed within one month of reaching minimum sample size estimated by power analysis. Families were recruited and randomized from August 2017 to October 2018; data collection continued through March 2019.

Study Conditions

Clinical Assessment (CA)

CA entailed the standard intake assessment procedures used in the county-funded behavioral parenting program. This included a parent interview regarding the child's developmental milestones, educational history, medical history, disruptive behavior symptoms, previous treatment experiences, and current parenting strategies. A series of observational parent–child interaction tasks followed.

CFI+CA

Caregivers in CFI+CA participated in an augmented CA that also included the core CFI (CFI; American Psychiatric Association [APA], 2013). The CFI is a brief (16-item) semi-structured interview designed for providers to assess a patient's cultural identity and how it might affect key aspects of their understanding of mental health difficulties and clinical care. The CFI assesses the patient's individual symptom experience, their perceptions of mental health, and their perceptions and experiences of treatment via four domains: (1) cultural definition of the problem, (2) cultural perceptions of cause, context, and support, (3) cultural factors affecting self-coping and past help seeking, and (4) cultural factors affecting current help seeking (American Psychiatric Association [APA], 2013). See Table 2 for the domains of the CFI and the main component sections. For CFI+CA cases, providers administered the CFI prior to the CA, consistent with its implementation guidelines in DSM-5 (American Psychiatric Association [APA], 2013). This decision to deliver the CFI first was made to remain consistent with previous studies (Aggarwal et al., 2020), enhance fidelity by having a clear implementation plan (Aggarwal et al., 2014), center caregiver values and perspectives from the beginning of the intake (La Roche, 2018), and increase rapport (Aggarwal et al., 2015, 2016b).

Providers, Setting, and Training

Providers in the current study who conducted all baseline clinical assessments and subsequent services ($N = 4$) were master's- or doctoral-level community practitioners providing clinical services within three community clinics that were embedded within neighborhood centers regularly accessed by the community (i.e., afterschool care centers, family and neighborhood resource programs). The providers were employed by the medical center (i.e., not affiliated with the PI) to provide services within the neighborhood centers. Three out of the 4 providers had not

delivered PCIT prior to the start of the study. They were trained by a certified trainer as part of the county-funded program to provide PCIT to underserved communities prior to delivering PCIT. These providers did not work for the PI or the study. The services were provided via a partnership between a medical center and the three neighborhood centers. Three of the providers were fluent in Spanish and delivered services in both English and Spanish. Providers conducted both CA and CFI+CA assessments. Randomization occurred at the patient rather than the provider level due to the providers working at three distinct community centers within distinct neighborhoods. Providers were masked to study hypotheses, but not study condition. For each family, the same provider conducted their intake assessment and their subsequent PCIT services. Providers and their supervisors at participating clinics completed a two-hour CFI training led by the study PI (who trained with one of the CFI developers) and another senior psychologist with CFI training experience. Per recommendations (Aggarwal et al., 2016a), training consisted of reviewing the CFI's written guidelines, a video demonstration, role-plays with feedback, a discussion of possible barriers to implementation, and peer debriefing exercises to consider implementation issues in their organizational climate. To prevent integrity drift and contamination across conditions, providers received structured feedback based on fidelity ratings from their first case prior to seeing study cases (Aggarwal et al., 2014). Three additional CFI booster trainings were implemented to problem solve any challenges with implementing the CFI (e.g., wording of the questions, using examples to increase caregiver responses).

Measures

Patient forms were administered through a secure online platform, or by paper when families preferred. Measures were available in English and Spanish.

Demographics

Primary caregivers reported on child and caregiver age, race, and ethnicity. Additionally, specific details regarding country of origin and immigration status were not collected to protect the privacy of families during a time of considerable increase in Immigrations and Custom Enforcement raids in the community where this study occurred. Caregivers also reported on their education, annual household income, and family size. Income-to-needs (INR) ratios were computed reflecting household income relative to the poverty threshold, and categorized as "extreme poverty" (INR \leq .5), "poor" (.5 $<$ INR \leq 1), "low-income" (1 $<$ INR \leq 2), "adequate-income" (2 $<$ INR \leq 4), and "affluent" (INR $>$ 4). To assess housing security, caregivers were asked two items from the U.S. Department of Housing and Urban Development: 1) *During the past year, have you had more than 2 people per bedroom*, and 2) *In the past year, have you temporarily lived with other people because of economic difficulties?* In addition, the *Everyday Stressors Index* (ESI; Hall, 1990), a 20-item measure of daily stressors experienced by economically disadvantaged caregivers with young children, was administered at intake. Items are rated on a Likert-style scale ranging from 1 = "not at all bothered" to 4 = "bothered a great deal," as well as "I don't know" = 0, and tallied with higher scores indicating greater daily stress (maximum score = 80). The ESI has demonstrated good internal consistency and construct validity in English- and Spanish-speaking samples (Hall et al., 1996; Gómez et al., 2015; Hall, 1990) ($\alpha = .79$ in present sample).

Intake Assessment Length

Providers recorded the total time, in minutes, spent completing each family's intake assessment. The pretreatment assessment sessions included the consent procedures, and CA or CFI+CA (depending on randomization). Time spent across the intake assessment was measured by provider report of the total length, in minutes, to complete these procedures. The pretreatment assessment typically lasted between 2 and 3 sessions.

Implementation Outcomes

Provider fidelity and condition integrity. To measure CFI fidelity and potential cross-condition contamination in CA, the CFI Fidelity Instrument (CFI-FI; Aggarwal et al., 2014) was used to code assessments in both conditions. Independent evaluators (IEs) masked to condition, study design, and study hypotheses coded recordings of all assessments. IEs met 80% reliability on a study video prior to coding further study videos. Consistent with previous research (Aggarwal et al., 2014), interrater reliability across IEs on a random 20% of study cases was high (i.e., agreement range: 80%–100% on Adherence items; mean agreement = 96.25%).

Provider perceptions of clinical utility. The *CFI Clinician Questionnaire* is a 4-item measure adapted from previous work (Aggarwal et al., 2015) to assess provider perceptions of CFI clinical utility. Directly following pretreatment assessment, providers rated 4 items related to content and quality of information, relationship with caregiver, treatment planning, and differential diagnosis (e.g., *“How much of an impact did using the CFI have on your relationship with your patient?”*) on a Likert-style scale ranging from 1 = “not at all” to 5 = “very much” (α in present sample = .84).

Perceptions of provider understanding of caregiver values and satisfaction. Two items developed for this study, administered directly after the intake assessment (but before treatment began), measured caregiver and provider perceptions of how well the provider understood the family’s values and what is important to them, and how satisfied they were with the intake assessment. The items were rated independently by caregivers and providers on a 5-point scale (1 = *not at all*; 5 = *very much*). The items were translated into Spanish and then back translated into English to ensure semantic and cultural accuracy.

Treatment Engagement

The behavioral domains of engagement (e.g., attendance and homework) were measured for each family via provider logs recording: (a) initial treatment session attendance (i.e., did family attend a first treatment session after completing intake assessment?), (b) weekly session attendance rate (percentage of sessions attended across weeks in treatment), (c) completion of first treatment module (i.e., caregiver acquisition of positive-attending skills), and (d) homework completion (i.e., mean percentage of weekly homework completed across weeks engaged in treatment). While the average PCIT treatment length is between 12 and 20 sessions, the length of treatment varies based on family’s specific needs, symptom reduction, and caregiver skill acquisition (PCIT International, n.d.).

The relationship domain of engagement was measured by the *Working Alliance Inventory-Short Form Revised* (WAI-SR; Hatcher & Gillaspy, 2006), administered at midtreatment. The WAI-SR is a 12-item caregiver-report of therapeutic alliance that assesses (a) perceived agreement with the provider on the tasks of therapy, (b) perceived agreement with the provider on the goals of therapy, and (c) the perceived affective bond between the provider and patient/ family. Items are rated on a 5-point Likert-style scale ranging from 1 = “never” to 5 = “always” and are summed for a total score. The WAI-SR has demonstrated strong internal consistency and construct and convergent validity in English and Spanish (Andrade- Gónzalez & Fernández-Liria, 2016; Hatcher & Gillaspy, 2006; Munder et al., 2010) (α = .94 in the present sample).

Treatment Response

Families were classified as Treatment Responders in accordance with formal PCIT graduation criteria (Eyberg & Funderburk, 2011), that is: (a) caregivers demonstrated skill acquisition, as coded against specific criteria in both phases of treatment; and (b) child behavior problems dropped into the subclinical range – i.e., *Eyberg Child Behavior Inventory* (ECBI) falls below 114; Eyberg, 1999).

Data Analysis

Intent-to-treat analyses were employed. Missing data were addressed through Multiple Imputation in Mplus (Enders, 2010). The majority of variables were completed for more than 90% of cases. Descriptive analyses were conducted to assess the implementation outcomes of fidelity, clinical utility, provider and caregiver perceptions of understanding the caregivers' values, and satisfaction with the intake. Additionally, linear regressions tested condition effects on caregiver and provider satisfaction, and the extent to which the provider understood the caregivers' values or what is important to them. Next, logistic and linear regressions examined condition effects on subsequent treatment engagement and response. Exploratory moderation analyses examined the main and interactive effects of language of service delivery (English versus Spanish) with study condition (CA versus CFI+CA) on dependent variables. To interpret effects, adjusted odds ratios and probabilities were calculated for logistic regressions and Cohen's d effect sizes were calculated for linear regressions. An alpha threshold of .25 determined inclusion of covariates. Due to condition differences all analyses controlled for length of intake assessment (in minutes), site, caregiver race/ethnicity, daily stress, and language of assessment delivery. Length of intake assessment is also controlled for to account for differences in effects solely related to differences in the amount of time the provider spent with the caregiver. Baseline ECBI score was included as a covariate for the treatment response analyses.

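### A total of 82 participants gives about 53–57% power for an odds ratio of 2.5, not the stated 80%

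*Combined protocol and SAP*

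**What the plan says.** The sample size rests on one sentence under Procedures. Its inputs are "A power analysis assuming an alpha level = 0.05, beta = 0.2, and power = 0.8", and its result is that the calculation "identified a sample ≥ 82 participants was needed to identify small-to-medium effects (i.e., OR~2.5"). It does not give the outcome, control event rate, sidedness, allocation ratio, test, or any allowance for covariates or dropout.

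The next sentence makes the number operative: "Recruitment was closed within one month of reaching minimum sample size estimated by power analysis". Under Participants the achieved sample is given: "Participants were 89 children ages 2–7". Together these show that 82 is a total over both conditions and not a number per arm.

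Under Data Analysis, "logistic and linear regressions examined condition effects on subsequent treatment engagement and response", so an odds ratio here compares two randomized groups on a binary outcome. Three outcomes under Treatment Engagement and Treatment Response are binary: attendance at a first treatment session, completion of the first module, and responder status.

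**The concern.** Comparing two groups on a yes/no outcome at an odds ratio of 2.5 normally takes about 80 participants in each arm. A total of 82 is about half of that. The control rate is not stated, so the question is whether any control rate could justify 82.

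The number decided when recruitment stopped, and it is the only statement of what the trial could detect. A reader who accepts 80% power could take a non-significant result on first-session attendance, module completion or treatment response as evidence against an odds ratio of 2.5. If true power is near one half, such a result says little.

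**Working it through.** **Inputs.** From Procedures: alpha 0.05, power 0.80, odds ratio 2.5, total 82. From Participants: 89 achieved. Assumed because not stated: two-sided test and 1:1 allocation (the most favourable ratio). The control rate p₁ was scanned from 2% to 97%.

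**Formulas.** The second rate is p₂ = 2.5p₁ / (1 − p₁ + 2.5p₁). With p̄ = (p₁ + p₂)/2, A = √(2p̄(1 − p̄)) and B = √(p₁(1 − p₁) + p₂(1 − p₂)):

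- n per arm = [(1.960·A + 0.842·B) / (p₂ − p₁)]²
- power = Φ{[(p₂ − p₁)√n − 1.960·A] / B}

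**Near the most favourable case, p₁ = 0.40.** p₂ = 1.00/1.60 = 0.625, p̄ = 0.5125, A = 0.7069, B = 0.6888.

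- n = [(1.3855 + 0.5797)/0.225]² = 76.3, so 77 per arm and 154 in total.
- Power at 41 per arm = Φ[(0.225 × 6.403 − 1.3855)/0.6888] = Φ(0.080) = 0.532.

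**Across control rates, odds ratio 2.5, two-sided:**

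| Control rate | Second rate | Power, N = 82 | Power, N = 89 | Total N for 80% |
|---|---|---|---|---|
| 10% | 21.7% | 0.30 | 0.33 | 302 |
| 20% | 38.5% | 0.45 | 0.48 | 190 |
| 30% | 51.7% | 0.52 | 0.55 | 160 |
| 40% | 62.5% | 0.53 | 0.57 | 154 |
| 50% | 71.4% | 0.51 | 0.55 | 162 |
| 60% | 78.9% | 0.46 | 0.49 | 184 |
| 70% | 85.4% | 0.38 | 0.41 | 230 |
| 80% | 90.9% | 0.29 | 0.31 | 326 |

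No control rate gives a total near 82, so the plan's figure is not reproduced.

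**Other tests and settings.**

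- Maximum power at 41 per arm: 52.4% by the Wald test on the log odds ratio and 53.8% by the arcsine method. At a control rate of 39%, exact power is 56.9% for chi-square and 47.9% for Fisher's test.
- One-sided: at most 65.7%, with a minimum total of 120.
- Unequal allocation: minimum total 160 at 1.5:1 and 171 at 2:1.

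**What 82 can detect.** Solving the power formula for the odds ratio at 41 per arm and 80% power gives about 3.5–3.8 at control rates of 30–50%, and 6.2 at 70%.

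**Continuous outcomes.** An odds ratio of 2.5 corresponds to d = ln(2.5)·√3/π = 0.505. With 82 in total, power for that d is about 62% two-sided and 73–74% one-sided; 62 per arm (124 in total) would be needed. A total of 82 gives 80% two-sided power for d of about 0.63.

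**Covariates.** Every model adjusts for variables that differed by condition, including intake length. If they explain a share R² of condition, the effective size is roughly 41(1 − R²) per arm. R² is not given. For R² of 0.1, 0.2 and 0.3 (assumed), best two-sided power is about 0.49, 0.44 and 0.40.

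**The case against.** The case for the plan has five parts.

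- **Sidedness.** The plan does not state it, and the hypotheses are directional: families given the added interview "would show higher rates of ultimate treatment response". So 53% is not an absolute ceiling. This stands as a caveat: exact chi-square gives about 57%, and a one-sided test at most 66%. Neither approaches 80%.
- **Origin of 82.** It matches the two-sided number per arm at control rates of about 25–54%, which suggests a per-arm figure taken as the total. Other slips are possible. A formula for a continuous predictor, with the odds ratio per standard deviation and an event rate near 13%, gives about 83. A linear-regression effect of f² = 0.10 gives 81, but that corresponds to d of about 0.63 and an odds ratio of about 3.1. Neither fits a binary condition at an odds ratio of 2.5. The document does not show where 82 came from, so the per-arm explanation is only an inference.
- **Covariates.** Silence about an allowance does not prove that none was made, and the loss cannot be sized from the document. That is correct, and the main result does not use it.
- **Scope.** Several outcomes are continuous, and there the shortfall is smaller. This stands, but about 62% is still well below 80%, and the plan expresses its target as an odds ratio.
- **Timing.** Recruitment ended in October 2018 and data collection in March 2019. The document also reports adjusted odds ratios and effect sizes to aid interpretation. So the remedy is limited to reporting. It still matters, because the Data Analysis section mentions no confidence intervals and the stated power is wrong.

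**Conclusion.** The concern holds. The stated alpha, power, odds ratio and sample size contradict one another by nearly a factor of two: at least 154 participants are needed where 82 are claimed. The conclusion does not depend on the missing control rate, because the shortfall is present at the most favourable value. The headline 53% (56.7% with 89 enrolled) assumes a two-sided test, 1:1 allocation and the pooled two-proportion formula. Changing the test or sidedness moves the best case to between 48% and 66%. High or low control rates reduce power further, and so would any association between the covariates and condition.

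**What to change.** Replace the power sentence under Procedures with one that:

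- names the outcome, control rate, sidedness and test assumed;
- states that 82 in total gives about 50–55% two-sided power for an odds ratio of 2.5 at control rates of 30–50%, with a best case of about 57% for the 89 enrolled;
- states that 82 gives 80% power only for odds ratios of about 3.5–3.8 at those control rates, or d of about 0.63 for continuous outcomes;
- says whether any allowance was made for covariates.

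In Data Analysis, add 95% confidence intervals for the adjusted odds ratios and standardized differences. State that a non-significant binary result will be judged by whether its interval excludes 2.5, and not taken as absence of an effect of that size.

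The cost is a text correction and the reporting of intervals that the fitted models already supply. No enrolment, data collection or change of analysis model is required. The price is a less favourable power statement.

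### Every condition-effect model adjusts for intake length, which the CFI itself changes, so no analysis estimates the randomized effect of adding the CFI

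*Combined protocol and SAP*

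**What the plan says.** The Objectives section says the trial "evaluated the incremental utility of augmenting Clinical Assessment with the CFI". Data Analysis opens with "Intent-to-treat analyses were employed".

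The covariates are then fixed for every model: "Due to condition differences all analyses controlled for length of intake assessment (in minutes), site, caregiver race/ethnicity, daily stress, and language of assessment delivery". A second reason is given for length alone: it is "also controlled for to account for differences in effects solely related to differences in the amount of time the provider spent with the caregiver".

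On timing, Procedures says: "Presenting families completed informed consent, then were randomized across two parallel pre-treatment" assessment conditions, so assignment comes before the intake interview. On content, the section on intake assessment length says the pretreatment sessions comprised consent and whichever interview the family was assigned. It adds: "Time spent across the intake assessment was measured by provider report of the total length, in minutes, to complete these procedures". The CFI+CA section describes the experimental arm as the standard assessment plus a 16-item interview.

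No condition-effect model without intake length is described. No direct-effect or mediation target is defined, and no assumption about confounding of length and outcome is stated.

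**The concern.** Adjustment for a variable measured before randomization leaves the target of a randomized comparison intact. Adjustment for a consequence of assignment does not. Intake length is such a consequence here, because the CFI is an extra interview inside the time being counted. Three things follow.

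- Any benefit that works through longer contact is removed from the condition effect, although a clinic that adopts the CFI also adopts its minutes.
- Families with the same recorded minutes in the two arms are not alike. A CFI+CA family at a given length would tend to have had a shorter standard assessment than a CA family at that length. Unmeasured characteristics that affect both length and outcome, such as talkativeness or case complexity, are then no longer balanced by randomization.
- Length is correlated with condition, which inflates the standard error of the condition effect.

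At stake are the condition effects on satisfaction, perceived understanding, engagement and treatment response, that is, every odds ratio and Cohen's d offered as evidence for or against the CFI.

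**Working it through.** **Inputs.** From the documents: 89 families (Participants), alpha 0.05 (Procedures), and length in all models (Data Analysis). The documents print no intake minutes by arm, so there is no plan figure to reproduce. Assumed: equal arms, a two-sided test, a linear outcome with within-arm SD 1, no other covariates, and an intake longer under CFI+CA by s within-arm SD, with s from 0.5 to 1.5.

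**1. Precision.** With equal arms, the squared correlation between condition and length is R² = s²/(s² + 4). The variance of the condition coefficient is multiplied by 1/(1 − R²) = 1 + s²/4.

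| s | Variance factor | Increase in SE | 89 families are worth |
|---|---|---|---|
| 0.5 | 1.06 | 3% | 84 |
| 1.0 | 1.25 | 12% | 71 |
| 1.5 | 1.56 | 25% | 57 |

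If length has no relation to outcome, this is the only cost. For a true effect of 0.50 SD, power falls from about 0.65 to 0.62, 0.55 and 0.46 respectively.

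**2. Benefit through contact time.** Suppose the direct effect is 0.30 SD and each SD of length improves outcome by 0.20 SD, with no confounding. At s = 1 the total effect is 0.30 + 0.20 × 1 = 0.50. The length-adjusted coefficient targets 0.30.

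- Unadjusted: SE = √(4 × 1.04/89) = 0.216, power about 0.63.
- Adjusted: SE = √(4 × 1.25/89) = 0.237, power about 0.24.

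Simulation with 4,000 replicates gave estimates of 0.49 and 0.30, and power of 0.62 and 0.23.

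**3. Confounding of length and outcome.** Suppose an unmeasured family trait explains half the variance of length within arm and correlates c with outcome, and length itself has no effect. The within-arm correlation of length and outcome is r = √0.5 × c. The adjusted coefficient is shifted by −r × s, with SE = √(4(1 + s²/4)(1 − r²)/89).

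With a true effect of 0.50 and s = 1:

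- c = +0.3: r = 0.21, so the adjusted estimate is 0.50 − 0.21 = 0.29.
- c = −0.3: the adjusted estimate is 0.50 + 0.21 = 0.71.
- The unadjusted estimate stays at 0.50 in both cases.

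With no true effect, the chance of a significant adjusted result (noncentral t) is:

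| c | s = 0.5 | s = 1.0 |
|---|---|---|
| 0.1 | 5% | 6% |
| 0.2 | 6% | 9% |
| 0.3 | 8% | 15% |
| 0.5 | 14% | 35% |

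The model without length rejects about 5% of the time throughout. A separate simulation with a within-arm length–outcome correlation of 0.25 gave 8.6%, 18.7% and 29.4% at s = 0.5, 1 and 1.5.

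**The case against.** The strongest defence is that the adjustment was deliberate. The plan wanted the effect of CFI content net of time, and it says so. That is a legitimate question, but it concerns a direct effect. A regression on minutes answers it only if nothing unmeasured affects both length and outcome, and randomization does not secure that. The plan neither names this target nor states the assumption, and its objective asks something else. The reason given supports a secondary analysis, not the only one.

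Several narrower points stand in whole or in part.

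- Nothing suggests that families were analysed outside their assigned arm, so in the narrow sense the intent-to-treat label may be accurate. What is missing is an estimate of the effect of assignment, which that label leads a reader to expect.
- That the CFI lengthens intake is an inference from the design. The plan's reference to condition differences covers five covariates and gives no direction. Recorded minutes also include consent, which precedes randomization. The remaining minutes still follow assignment.
- Rapport is a poor example of a confounder, because the CFI was placed first partly to improve it. Daily stress, and baseline ECBI in the response models, may capture some case complexity.
- The larger error rates need a sizeable length difference and a strong trait. With weak inputs the distortion is small, as the table shows.
- The fall in power from 0.63 to 0.24 compares tests of two different effects, total and direct.
- The calculations are for linear outcomes without the plan's other covariates. Initial attendance, module completion and treatment response are binary. In logistic models, adding a covariate also changes what the odds ratio measures.

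**Conclusion.** The concern holds. That the length-adjusted coefficient is not the total effect of adding the CFI follows from the order of events and the content of the recorded time. It needs none of the numerical assumptions beyond the CFI taking time to deliver. It applies to every condition-effect model described.

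The size and direction of any distortion cannot be determined from the documents. Bias runs against the CFI if family traits raise both length and outcome, and in its favour if they lengthen intake but worsen outcome. Under the assumptions above, the consequences range from a 3% loss of precision with almost no bias to an estimate wrong by about 0.2 SD and a false-positive rate of 15% to 35%. Because this touches every reported condition effect and is easily corrected, it should be fixed before the results are read as the effect of the CFI.

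**What to change.** Remove intake length from all main condition-effect models, including the language-moderation models, and adjust only for variables fixed before randomization. Report these as the intent-to-treat results.

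Confirm when daily stress was recorded. The scale was given at intake, and study questionnaires are part of an intake that follows randomization. If it was completed after the assigned interview began, the same rule applies to it.

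If contact time is of interest, keep the length-adjusted model as a labelled secondary direct-effect or sensitivity analysis. State that it assumes no unmeasured common cause of length and outcome, and report intake minutes by arm beside it.

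The cost is a short revision of the Data Analysis text and a re-run of existing models on data already collected.
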